6.3.4 Follow-up for toxicities while receiving RAD001

Patients who interrupt or permanently discontinue RAD001 due to an adverse event or abnormal laboratory value must be followed at least weekly via telephone for 28 days after the last dose of RAD001, and subsequently at monthly intervals until resolution or stabilization of the event, whichever comes first. If a patient requires a RAD001 dose delay of > 21 days from the intended day of the next scheduled dose, then the patient should be discontinued from the study.

All patients will be followed for adverse events and serious adverse events for 28 days following the last dose of RAD001.

6.3.5 Other concomitant medications

Inhibitors of CYP3A4 and/or PgP

Co-administration with strong inhibitors of CYP3A4 (e.g., ketoconazole, itraconazole, ritonavir) or P-glycoprotein (PgP) should be avoided.

Co-administration with moderate CYP3A4 inhibitors (e.g., erythromycin, fluconazole) or PgP inhibitors should be used with caution. If patient requires co-administration of moderate CYP3A4 inhibitors or PgP inhibitors, reduce the dose of everolimus to half the currently used dose. Additional dose reductions to every other day may be required to manage toxicities. If

the inhibitor is discontinued the everolimus dose should be returned to the dose used prior to initiation of the moderate CYP3A4/PgP inhibitor.

Seville orange, star fruit, grapefruit and their juices affect P450 and PgP activity. Concomitant use should be avoided.

Inducers of CYP3A4 and/or PgP

Avoid the use of strong CYP3A4 inducers. If patient requires co-administration of strong CYP3A4 inducers (i.e., phenytoin, carbamazepine, rifampin, rifabutin, phenobarbital, St. John's wort), an increase in the dose of everolimus up to twice the currently used daily dose should be considered, using 5 mg increments every other day – 5 mg increments daily. Enzyme induction usually occurs within 7-10 days, therefore everolimus dose should be increased by one increment 7 days after the start of the inducer therapy. If no safety concerns are seen within the next 7 days, the dose can be increased again one additional increment up to a maximum of twice the daily dose used prior to initiation of the strong CYP3A4 inducer.

This dose adjustment of everolimus is intended to achieve similar AUC to the range observed without inducers. However, there are no clinical data with this dose adjustment in patients receiving strong CYP3A4 inducers. If the strong inducer is discontinued the everolimus dose should be returned to the dose used prior to initiation of the strong CYP3A/PgP inducer.

Table 6-7 Clinically relevant drug interactions: substrates, inducers, and inhibitors of isoenzyme CYP3A

INDUCERS
Barbiturates, carbamazepine, glucocorticoids, modafinil, oxcarbazepine, phenobarbital, phenytoin, pioglitazone, rifabutin, rifampin, St. John's wort, troglitazone, efavirenz, nevirapine, topiramate
INHIBITORS
Strong inhibitors: clarithromycin, conivaptan, indinavir, itraconazole, ketoconazole, lopinavir, mibefradil, nefazodone, nelfinavir, ritonavir, saquinavir, telithromycin, troleandomycin, voriconazole, Posaconazole (Krishna et al, 2009)
Moderate inhibitors: aprepitant, atazanavir, cimetidine, ciprofloxacin, darunavir, diltiazem, erythromycin, fluconazole, grapefruit juice, imatinib, tofisopam, verapamil,

Table 6-8 Clinically relevant drug interactions mediated by PgP

PgP Substrates	PgP Inhibitors in vivo	PgP Inducers
digoxin, fexofenadine, indinavir, vincristine, colchicine, topotecan, paclitaxel	amiodarone, azithromycin, captopril, carvedilol, clarithromycin, conivaptan, cyclosporine, diltiazem, elacridar, erythromycin, felodipine, (GF120918),	rifampin, St John's wort

PgP Substrates	PgP Inhibitors in vivo	PgP Inducers
	itraconazole, ketocoazole, lopinavir, (LY335979), mibefradil, nifedipine, nitrendipine, (PSC833), quinidine, ranolazine, ritonavir, talinolol, valsopodar, verapamil	

Reference:

Internal Clinical Pharmacology Drug-drug interaction (DDI) memo, updated Dec. 2, 2009, which summarizes DDI data from three sources including the FDA's "Guidance for Industry, Drug Interaction Studies, the University of Washington's Drug Interaction Database, and Indiana University School of Medicine's Drug Interaction Table. "

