6.3.2 RAD001 dose adjustments

For patients who are unable to tolerate the protocol-specified RAD001 dosing schedule, dose-adjustment guidelines are given below. Three RAD001 dose levels are defined for dose adjustment: 10mg daily, 5mg daily, and 5mg every other day. (Table – 1)

Table 6-1 RAD001 Dose levels for dose adjustment

Dose level	Dose and schedule
0 (starting dose)	10mg daily
Decrease 1 dose level	5mg daily
Decrease 2 dose levels	5mg every other day

Toxicity will be assessed using the NCI-CTC for Adverse Events, version 3.0 (CTCAE v3.0,

(<http://ctep.cancer.gov/forms/CTCAEv3.pdf>).

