6.3.3 Management of RAD001 toxicities

Known Undesirable Side Effects of RAD001

Adverse events most frequently observed with RAD001 are rash, stomatitis/oral mucositis, fatigue, headache, anorexia, nausea, vomiting, diarrhea, ocular toxicity and infections. Non-infectious pneumonitis has also been observed. Overall, the most frequently observed laboratory abnormalities include neutropenia, thrombocytopenia, hypercholesterolemia, and/or hypertriglyceridemia. The majority of these AEs have been of mild to moderate severity (CTC grade 1-2).

Table 6-2 Criteria for dose-modification in case of suspected RAD001 toxicity and re-initiation of RAD001 treatment

Toxicity	Actions
Non-hematological toxicity Grade 2 (except pneumonitis, refer to Table 6.3)	If the toxicity is tolerable to the patient, maintain the same dose. If the toxicity is intolerable to patient, interrupt RAD001 until recovery to grade \leq 1. Then reintroduce RAD001 at same dose. If event returns to grade 2, interrupt RAD001 until recovery to grade \leq 1. Then reintroduce RAD001 at the lower dose level.
Grade 3 (except hyperlipidemia)	Interrupt RAD001 until recovery to grade \leq 1. Then reintroduce RAD001 at the lower dose level. For pneumonitis, consider the use of a short course of corticosteroids (see table 6.3).
Grade 3 hyperlipidemia (hypercholesterolemia and/or hypertriglyceridemia)	Should be managed using standard medical therapies.
Grade 4	Discontinue RAD001.
Hematological toxicity Grade 2 Thrombocytopenia (platelets $<$ 75, \geq 50x10 ⁹ /L)	Interrupt RAD001 until recovery to grade \leq 1 (platelets \geq 75x10 ⁹ /L). Then reintroduce RAD001 at initial dose. If thrombocytopenia again returns to grade 2, interrupt RAD001 until recovery to grade \leq 1. Then reintroduce RAD001 at the lower dose level.
Grade 3 Thrombocytopenia (platelets $<$ 50, \geq 25x10 ⁹ /L)	Interrupt RAD001 until recovery to grade \leq 1 (platelets \geq 75x10 ⁹ /L). Then resume RAD001 at one dose level lower. If grade 3 thrombocytopenia recurs, discontinue RAD001.
Grade 4 Thrombocytopenia (platelets $<$ 25x10 ⁹ /L)	Discontinue RAD001.

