Grade 3 Neutropenia (neutrophils $< 1, \geq 0.5 \times 10^9/L$)	Interrupt RAD001 until recovery to grade ≤ 1 (neutrophils $\geq 1.5 \times 10^9/L$). Then resume RAD001 at the initial dose. If ANC again returns to Grade 3, hold RAD001 until the ANC $\geq 1.5 \times 10^9/L$. Then resume RAD001 dosing at the lower dose level. Discontinue patient from study therapy for a third episode of grade 3 neutropenia.
Grade 4 Neutropenia (neutrophils $< 0.5 \times 10^9/L$)	Interrupt RAD001 until recovery to grade ≤ 1 (neutrophils $\geq 1.5 \times 10^9/L$). Then resume RAD001 at the lower dose level. If grade 3 or grade 4 neutropenia occurs despite this dose reduction, discontinue RAD001.
Grade 3 febrile neutropenia (not life-threatening)	Interrupt RAD001 until resolution of fever and neutropenia to grade ≤ 1 . Hold further RAD001 until the ANC $\geq 1,500/mm^3$ and fever has resolved. Then resume RAD001 at the lower dose level. If febrile neutropenia recurs, discontinue RAD001.
Grade 4 febrile neutropenia (life-threatening)	Discontinue RAD001.
Any hematological or non-hematological toxicity requiring interruption for ≥ 3 weeks	Discontinue RAD001.

Monitoring of RAD001 suspected toxicities

Patients whose treatment is interrupted or permanently discontinued due to an adverse event or abnormal laboratory value suspected to be related to RAD001 must be followed at least weekly via telephone until the adverse event or abnormal laboratory value resolves or returns to grade 1. If a patient requires a dose delay of > 21 days from the intended day of the next scheduled dose, then the patient must be discontinued from the study.

Management of stomatitis/oral mucositis/mouth ulcers

Stomatitis/oral mucositis/mouth ulcers due to RAD001 should be treated using local supportive care. Please note that investigators in earlier trials have described the oral toxicities associated with RAD001 as mouth ulcers, rather than mucositis or stomatitis. If your examination reveals mouth ulcers rather than a more general inflammation of the mouth, please classify the adverse event as such. Please follow the paradigm below for treatment of stomatitis/oral mucositis/mouth ulcers:

1. For mild toxicity (grade 1), use conservative measures such as **non-alcoholic mouth wash or salt water (0.9%) mouth wash** several times a day until resolution.

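### Section 6.3.5 (interacting drugs) and Tables 6-1 and 6-2 (toxicity) are not reconciled for a patient who needs both kinds of RAD001 dose adjustment

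*Protocol*

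**What the plan says.** Protocol section 6.3.2 fixes the scale: "Three RAD001 dose levels are defined for dose adjustment: 10mg daily, 5mg daily, and 5mg every other day". Table 6-1 labels the first of these level 0, the starting dose. Section 6.2 supplies 5 mg tablets only.

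Table 6-2 (section 6.3.3) sets the restart dose once a toxicity has recovered to grade 1 or better:

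- Grade 3 non-hematological toxicity other than hyperlipidemia: "Then reintroduce RAD001 at the lower dose level. For pneumonitis, consider the use of a short course of corticosteroids".
- Grade 3 thrombocytopenia: "Then resume RAD001 at one dose level lower. If grade 3 thrombocytopenia recurs, discontinue RAD001".
- First grade 2 thrombocytopenia: "Then reintroduce RAD001 at initial dose".
- First grade 3 neutropenia: "Then resume RAD001 at the initial dose. If ANC again returns to Grade 3", followed by a step down at the second episode.
- Intolerable grade 2 non-hematological toxicity, first episode: restart at the *same* dose, a different word from *initial*.

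For a moderate CYP3A4 inhibitor or a PgP inhibitor, section 6.3.5 tells the site to "reduce the dose of everolimus to half the currently used dose". It adds: "Additional dose reductions to every other day may be required to manage toxicities". The next sentence is the return rule: if "the inhibitor is discontinued the everolimus dose should be returned to the dose used prior to initiation of the moderate CYP3A4/PgP inhibitor". For an unavoidable strong inducer, an increase to as much as twice the dose in use is to be considered, and the pre-inducer dose is resumed when the inducer stops.

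Neither set of rules refers to the other, and no passage says which prevails.

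**The concern.** Each rule set is written as if it were the only reason for changing the dose. When both apply, following the second instruction can cancel the first, or can call for a dose level that Table 6-1 does not contain. This matters first for patient safety, because a reduction required by Table 6-2 can be reversed by a rule that does not mention it. It also matters for uniform conduct, because two sites could give the same patient different doses and both could point to the protocol. A lesser consequence falls on the descriptive tables of mean dose and of dose changes by reason (protocol 10.3, SAP 1.3), which are harder to interpret if the rules behind the changes are ambiguous.

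**Working it through.** The plan states no figure on this point, so the check is dose arithmetic on its own rules. Mean daily doses of the Table 6-1 levels are 10 mg; 5 mg; and 5 mg every other day = 5/2 = 2.5 mg.

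**(a) Inhibitor stopped after a toxicity reduction.**

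1. Start: 10 mg/day.
2. Moderate inhibitor started (6.3.5): 10 × 0.5 = 5 mg/day.
3. Grade 3 non-hematological toxicity, recovery, one level down (Table 6-2): 2.5 mg/day.
4. Inhibitor stopped (6.3.5): back to 10 mg/day.

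Prescribed dose on return, relative to the reduced dose: 10/2.5 = 4. Relative to the dose at which the toxicity occurred: 10/5 = 2.

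Prescribed dose is not exposure, because the inhibitor is withdrawn at step 4. Let the inhibitor multiply exposure by *f*, with exposure proportional to dose (section 1.3.2 reports a dose-proportional AUC). The documents give no *f*; halving the dose would offset *f* = 2. Then

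- return versus reduced state = 10/(2.5 × *f*) = 4/*f*
- return versus state at toxicity = 10/(5 × *f*) = 2/*f*

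| *f* (assumed) | Return vs reduced | Return vs at toxicity |
|---|---|---|
| 1.5 | 2.67 | 1.33 |
| 2 | 2.00 | 1.00 |
| 3 | 1.33 | 0.67 |
| 4 | 1.00 | 0.50 |

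At *f* = 2 the return restores exactly the exposure at which the toxicity occurred, so the Table 6-2 reduction is cancelled. Below 2 the return exceeds that exposure. Above 2 part of the reduction survives, and at *f* = 4 all of it does.

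**(b) *Initial dose* in Table 6-2.** Take a patient at 5 mg daily, either because an inhibitor is continuing or because of an earlier toxicity reduction, who has a first grade 2 thrombocytopenia or first grade 3 neutropenia.

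- If the term means level 0 of Table 6-1: 5 to 10 mg, and 10/5 = 2-fold. This cancels the inhibitor halving while the inhibitor continues, or cancels the earlier reduction.
- If it means the dose held before the interruption: 5 to 5 mg, no rise.

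**(c) Below the scale.** Halving 5 mg every other day gives 2.5/2 = 1.25 mg/day on average. Table 6-1 has no such level. Table 6-5 (hepatitis B) does say what happens to a patient already on the lowest dose; section 6.3.5 has no counterpart.

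**(d) Above the scale.** The strong-inducer rule can lead from 10 to at most 10 × 2 = 20 mg/day. Table 6-1 stops at 10 mg, so *lower dose level* is undefined for a patient raised above it. The inducer stop rule also makes no exception for an intervening toxicity reduction; because the step down from above 10 mg is undefined, no multiple is given for it.

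**The case against.** The strongest reply is that (a) shows silence rather than contradiction. Table 6-2 acts at restart and section 6.3.5 acts when the inhibitor stops. These are successive events, both instructions can be carried out in turn, and nothing in Table 6-2 forbids later re-escalation. Section 6.3.5 even foresees toxicity reductions during inhibitor use before it states the return rule, so the sequence may be intended. It is true that the lead case is not literally impossible to follow. But the section that foresees the reduction then gives a return rule with no exception for it, and Table 6-2 provides no way back up. Whether the return is meant to override a Table 6-2 reduction is not stated.

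A reader might infer that the rules quadruple exposure just after a serious toxicity. The documents do not support that:

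- The 4-fold figure is prescribed milligrams.
- Restart requires recovery to grade 1 or better, and nothing ties the stopping of the inhibitor to that moment.
- Grade 2 thrombocytopenia, one of the two triggers in (b), is not shown to be serious.
- The 2-fold rise in (b) depends on one reading of an undefined term. Tables 4-1 and 6-1 say *starting* dose, so *initial* may mean something else.
- Cases (c) and (d) are missing levels, not one rule undoing another.

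Reach is also narrow. Users of interacting drugs are excluded at entry unless the drug is necessary and has no substitute. Moderate inhibitors call for caution, and strong inducers are to be avoided. The inducer increase is only to be considered, and its second increment requires the absence of safety concerns. The Amendment 7 rationale reports enrollment complete and two patients on drug at 23 July 2013. The investigator's duty to stop for significant safety risk (6.3.6) gives protection but does not rank the two dose rules.

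The effect on analysis is small: doses and changes are recorded on the CRF, the tables are descriptive, and the efficacy decision rule does not use them.

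**Conclusion.** The point holds as a failure to reconcile two sets of dosing rules, and it should be corrected. In case (a), following section 6.3.5 as written raises the prescribed dose 4-fold over the toxicity-reduced dose. The corresponding exposure rise is about 2-fold if *f* = 2, and 2.67-fold down to none for *f* from 1.5 to 4; *f* is assumed throughout. Case (b) is an undefined term, with a 2-fold rise on one reading and none on the other. Cases (c) and (d) are gaps in the dose scale. The documents give no count of affected patients, but the restrictions on interacting drugs suggest few. No conclusion about the trial's efficacy result follows from this.

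**What to change.** The sponsor's clinical team should reconcile section 6.3.5 with Tables 6-1 and 6-2 by amendment. The text should:

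- define *initial dose* in Table 6-2;
- state which rule governs when an interaction adjustment and a toxicity reduction are both in force, including when the inhibitor or inducer is stopped after an intervening toxicity reduction;
- state how patients whose dose falls below or above the Table 6-1 levels are handled.

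The choice of rule and dose belongs to that team; none is proposed here. The cost is amendment wording and its approval, with no new procedures or data. Amendment 7 already reopened the inducer paragraph of section 6.3.5.

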****This list of clinically relevant drug interactions is updated as of December 02, 2009****

6.3.6 Study drug discontinuation

Study drug must be discontinued for a given patient if the investigator determines that continuing it would result in a significant safety risk for that patient. Patients who, in the opinion of the investigator, require alternative medical therapy, will be discontinued from the study. Patients with a progression will be discontinued from the study. Patients who become pregnant during the study must be withdrawn. If the treatment has to be interrupted for more than 21 consecutive days for any reason, the patient will be discontinued from the study unless otherwise discussed with the study coordinator. In case of patient's discontinuation, the end of study evaluation will be completed as soon as possible. End of study evaluations will include adverse events, concomitant medications and therapies, physical examination, vital signs, ECOG performance status, biochemistry, hematology and tumor measurement.

Patients who discontinue prematurely due to significant AE should continue to be followed-up until resolution of the AE, and the relevant sections of the CRF should be completed as appropriate. Patients who are discontinued due to clinically significant abnormalities in clinical laboratory results should continue to be evaluated until the abnormality resolves or is judged to be permanent.

It will be documented whether or not each patient completed the clinical study. If, for any patient, the study treatment was discontinued the reason will be recorded. Reasons that a patient may discontinue participation in a clinical study are considered to constitute one of the following:

1. Adverse event(s)
2. Abnormal laboratory value(s)
3. Abnormal test procedure result(s)
4. Unsatisfactory therapeutic effect
5. Subject's condition no longer requires study treatment

6. Protocol violation which affect the safety of the patient
7. Subject withdraws consent
8. Lost to follow-up
9. Administrative problems
10. Death

Progressive disease is defined as unsatisfactory therapeutic effect.

For patients who are lost to follow-up, the investigator should show “due diligence” by documenting in the source documents steps taken to contact the patient, e.g. dates of telephone calls, registered letters, etc.

It is agreed that for reasonable cause, either the investigator or Novartis may terminate this study, provided a written notice is submitted at a reasonable time in advance of the intended termination.

A Study Drug Discontinuation form should be completed, giving the date and primary reason for stopping the study drug.

Study treatment will be continued until progression. Patients will be followed until progression.

The overall survival will be documented on the survival information page for all patients except for those who withdrew consent or are lost to follow-up.

7 Visit schedule and assessments

7.1 Information to be collected on screening failures

Information on screening failures will be kept in the Novartis Screening Failure Log. No CRF has is needed for screening failures.

All data obtained from the assessments listed in Table 1 and described in detail in the subsections below must be supported in the patient’s source documentation. Assessments that generate data for database entry and which are recorded on CRFs are listed using the CRF name. Assessments that are transferred to the database electronically (e.g. laboratory data) are listed by test name.

The final examination (visit 6 respectively EOS) will be performed for all patients included in this trial (i.e. who signed an informed consent form and received study treatment), whether they discontinued study treatment prematurely or completed the study treatment. Patients who discontinue study drug before completing the core study, and those who prematurely withdraw from the core study for any reason, should be scheduled for the End-of-study-visit as soon as possible, at which time all of the assessments listed for the EOS-visit will be performed.

During the follow-up period, the treatment regimen as taken during the study should be maintained. However, changes in the regimen based on each patient’s clinical needs and the investigators’ experience and discretion will be possible at any time. In the Follow-Up-Phase

	Base-line ¹	Core study						Follow-up ¹²				End of FUP
Visit No.	1	2	3	4	5	6	EOS	FUP 1 - X				
Day	-14	1										
Week			4	8	12	16		28	40	52	X	
Tumor evaluation (RECIST) ⁷	x			x		x	x	x	x	x	x	
Study drug administration		x	x	x	x	x		x	x	x	x	
Adverse events ⁸	x	ongoing data capture						ongoing data capture				
Prior medication	x											
Concomitant medication	x	ongoing data capture						ongoing data capture				
Survival-information ¹⁰												x
Comments		ongoing data capture						ongoing data capture				

¹Described in Section 7.2; 7.5.2

²Described in Section 7.5.3

³Described in Section 7.5.4

⁴Described in Section 7.5.5

⁵Described in Section 7.5.7; 8.2

⁶Described in Section 7.5.6

⁷Described in Section 7.4

⁸Described in Section 8.1.1

⁹Chest x-ray only in cases where no CT/MRI thorax is available

¹⁰Survival information for patients who discontinued earlier

¹¹ Baseline assessment can be done between day-14 and day 1 together with visit 2

¹² During the follow up period patients will continue to be followed every 3 months until progression

X All patients should be screened for hepatitis risk factors and any past illnesses of hepatitis B and hepatitis C. It is highly recommended that patients positive HBV-DNA or HBsAg are treated prophylactically with an antiviral for 1-2 weeks prior to receiving study drug. The antiviral treatment should continue throughout the entire study period and for at least 4 weeks after the last dose of study drug. Patients with viral hepatitis C risk factors should be screened for HCV RNA-PCR.

XX Patients on antiviral prophylaxis treatment or positive HBV antibodies should be tested for HBV-DNA according to study visit schedule. Patients with positive HCV-RNA PCR or a history of past infection, even if treated and considered 'cured' – should be followed by HCV-RNA PCR according to visit schedule.

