The investigator should promote compliance by instructing the patient to take the study drug exactly as prescribed and by stating that compliance is necessary for the patient's safety and the validity of the study. The patient should be instructed to contact the investigator if he/she is unable for any reason to take the study drug as prescribed.

All dosages prescribed and dispensed to the patient and all dose changes during the study must be recorded on the Dosage Administration Record CRF.

Management of Hepatitis reactivation

Monitoring and prophylactic treatment for hepatitis B reactivation

Table 4 provides details of monitoring and prophylactic therapy according to the baseline results of viral load and serologic markers testing.

Table 6-4 Action to be taken for positive baseline hepatitis B results

Test	Result	Result	Result	Result	Result
HBV-DNA	+	+ or -	-	-	-
HBsAg	+ or -	+	-	-	-
HBs Ab	+ or -	+ or -	+ and no prior HBV vaccination	+ or -	- or + with prior HBV vaccination
HBc Ab	+ or -	+ or -	+ or -	+	-

Test	Result	Result	Result	Result	Result
Recommendation	Prophylaxis treatment should be started 1-2 weeks prior to first dose of study drug Monitor HBV-DNA approximately every 4-8 weeks		No prophylaxis Monitor HBV-DNA approximately every 4 weeks		No specific action

Antiviral prophylaxis therapy should continue for at least 4 weeks after last dose of study drug.

For patients who have already been randomized and received study drug prior to the approval of the amendment, the same process should be followed at the patient's next visit. The first HBV-DNA result would be regarded as baseline.

For hepatitis B reactivation, definition and management guidelines, see Table 5 Guidelines for management of hepatitis B.

Table 6-5 Guidelines for management of hepatitis B

HBV reactivation (with or without clinical signs and symptoms)*	

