* All reactivations of hepatitis B are to be recorded as grade 3 (CTCAE v 3.0 Metabolic Laboratory/Other: Viral Re-activation), unless considered life threatening by the investigator; in which case they should be recorded as grade 4 (CTCAE v 3.0 Metabolic Laboratory/Other: Viral Re-activation). Date of viral reactivation is the date on which both DNA and ALT criteria were met (e.g. for a patient who was HBV-DNA positive on 01-JAN-10 and whose ALT reached $\geq 5 \times \text{ULN}$ on 01-APR-10, the date of viral reactivation is 01-APR-10).

Monitoring for hepatitis C

The following two categories of patients should be monitored every 4–8 weeks for HCV reactivation:

- Patients with detectable HCV RNA-PCR test at baseline.
- Patients known to have a history of HCV infection, despite a negative viral load test at baseline (including those that were treated and are considered ‘cured’)

For definition of hepatitis C reactivation and the management guidelines, see Table 6 Guidelines for management of hepatitis C.

Table 6-6 Guidelines for management of hepatitis C

HCV reactivation*	

For patients with baseline results: Detectable HCV-RNA, reactivation is defined as: ALT elevation x 5 ULN
	Discontinue study drug

For patients with baseline results: Knowledge of past hepatitis C infection with no detectable HCV-RNA, reactivation is defined as: New appearance of detectable HCV-RNA
	Discontinue study drug

- All reactivations of hepatitis C are to be recorded as grade 3 (CTCAE v 3.0 Metabolic Laboratory/Other: Viral Re-activation), unless considered life threatening by the investigator; in which case they should be recorded as grade 4 (CTCAE v 3.0 Metabolic Laboratory/Other: Viral Re-activation).

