7.2 Patient demographics/other baseline characteristics

Demographic data include: Date of birth, sex, and race.

Baseline characteristics include: Medical history/current medical condition, prior medication, tumor history, baseline tumor assessment, relevant prior tumor therapy, ECOG, vital signs (height, weight, blood pressure, pulse), result of pregnancy test, hematology and biochemistry.

HBV testing

Prior to starting study drug, the categories of patients listed in Section 4 Changes to Study design should be tested for hepatitis B serologic markers and viral load: HBV-DNA HBsAg, HBc Ab, and HBs Ab.

HBV DNA monitoring should be done depending on results from serologic markers and viral load as listed in Table 4.

HCV testing

Patients with hepatitis C risk factors and additional patients at the discretion of the investigator should be tested for HCV RNA-PCR test at baseline. For a list of hepatitis C risk factors, refer to Section 4 Changes to Study design.

Follow-up testing will be performed, as per the visit schedule, only if the patient has a history or is positive at baseline, or both.

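### After week 16, Table 7-1 footnote XX and the HCV sentence in 7.2 tie hepatitis testing to visits 12 weeks apart, wider than the intervals in 6.3.3 and Table 6-4

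*Protocol*

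**What the plan says.** The protocol sets the timing of hepatitis testing in several places. The SAP does not address it.

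**Tied to visits**
- Table 7-1, footnote XX, HBV: patients on prophylaxis or with HBV antibodies "should be tested for HBV-DNA according to study visit schedule".
- Table 7-1, footnote XX, HCV: patients with positive HCV-RNA or a past infection "should be followed by HCV-RNA PCR according to visit schedule".
- Section 7.2, HCV testing: "Follow-up testing will be performed, as per the visit schedule, only if the patient has a history or is positive at baseline, or both".

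**Given as intervals**
- Section 6.3.3, HCV: patients with detectable RNA at baseline or a history of infection "should be monitored every 4–8 weeks for HCV reactivation".
- Table 6-4, HBV without prophylaxis: "No prophylaxis Monitor HBV-DNA approximately every 4 weeks".
- Table 6-4, HBV on prophylaxis: "Monitor HBV-DNA approximately every 4-8 weeks".
- Section 7.2, HBV testing: "HBV DNA monitoring should be done depending on results from serologic markers and viral load as listed in Table 4". This points to what is now Table 6-4, so it agrees with 6.3.3.

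Table 7-1 places core visits at weeks 4, 8, 12 and 16 and follow-up visits at weeks 28, 40, 52 and X. Its footnote 12 describes follow-up as three-monthly until progression. Sections 6.3.6 and 7.1 keep patients on study drug through that period, and the study-drug row of Table 7-1 is marked in the follow-up columns.

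**The concern.** Two sets of instructions govern the same tests. They agree while visits are 4-weekly and diverge once visits spread out, although the patient is still taking an immunosuppressive drug. Sites commonly work from the assessment table, and here the table's own footnote leads to the sparser testing.

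What is at stake is how quickly a reactivation is recognised. Tables 6-5 and 6-6 require action when it occurs. For past HCV with undetectable RNA, study drug is discontinued. For antibody-positive HBV, study drug is interrupted and an antiviral started. Where the definition is a viral-load result and nothing else, that action cannot be triggered until the test is done.

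**Working it through.** **Inputs.** Visit weeks 4, 8, 12, 16, 28, 40, 52 (Table 7-1), with start of treatment taken as week 0; three-monthly follow-up (footnote 12); HCV interval 4 to 8 weeks (6.3.3); HBV-DNA interval about 4 weeks without prophylaxis, 4 to 8 weeks with it (Table 6-4).

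**Step 1: gaps between visits**
- Up to week 16: 4 − 0, 8 − 4, 12 − 8 and 16 − 12, each 4 weeks. Every stated interval is met.
- After week 16: 28 − 16, 40 − 28 and 52 − 40, each 12 weeks.
- Check against footnote 12: three months = 365.25 / (4 × 7) = 13.04 weeks, in line with columns 12 weeks apart.

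**Step 2: compare with the recommended intervals**
- HCV, and HBV on prophylaxis: 12 / 8 = 1.5 times the longest recommended interval.
- HBV without prophylaxis: 12 / 4 = 3 times the approximate interval.

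**Step 3: where a wide gap delays detection.** This depends on the definitions in Tables 6-5 and 6-6.

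| Baseline status | Reactivation defined by | Action | Delay shown? |
|---|---|---|---|
| HBV-DNA or HBsAg positive | HBV-DNA change and ALT elevation, both needed | Interrupt drug, add second antiviral | No: ALT timing after week 16 is not visible |
| HBV-DNA and HBsAg negative, antibody positive | HBV-DNA becoming measurable, alone | Interrupt drug, start antiviral | Yes: up to about 12 weeks, against about 4 |
| HCV-RNA detectable | ALT elevation, alone | Discontinue drug | No: PCR timing does not enter the definition |
| Past HCV, RNA undetectable | "New appearance of detectable HCV-RNA", alone | Discontinue drug | Yes: up to about 12 weeks, against 4 to 8 |

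The worst case is a reactivation just after one visit's test that is found only at the next, for example between weeks 16 and 28.

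**Step 4: number of tests after week 16, up to week 52 (36 weeks)**
- On the visit schedule: weeks 28, 40, 52 = 3.
- Every 4 weeks: 36 / 4 = 9.
- Every 8 weeks: 36 / 8 = 4.5, so at least 4 (weeks 24, 32, 40, 48).

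Three visit-based tests cannot meet either interval, so tests between visits are needed.

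**The case against.** The strongest reply is that this is loose cross-referencing, not a contradiction. Footnote XX states no interval and does not forbid testing between visits. Section 4 sends sites to 6.3.3 for both viruses, and 7.2 sends HBV monitoring to the hepatitis B table. A careful site can meet both texts. This largely stands, and it makes the HBV case the weaker one: a single footnote is out of line with two agreeing sections. For HCV, both the footnote and 7.2 give the looser rule. Meeting both texts still requires unscheduled draws that neither of those places asks for.

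A second reply is that the hepatitis rows of Table 7-1, and the rest of a sentence on the follow-up phase just before the table, are not visible in the text available. That is a real limit, and what is missing cannot be held against the plan. A row could mark cells in the existing columns or carry a text note, but it could not add a visit between weeks 16 and 28. Footnote 12 independently gives three-monthly follow-up.

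Third, the intervals are recommendations: 6.3.3 uses should, and Table 6-4 gives approximate spacing under a recommendation row. This stands. A reader might treat them as hard limits of 28 and 56 days and count breaches; the wording does not support that.

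A reader might also infer that every patient with hepatitis markers faces delayed detection. The definitions do not show this where ALT is part or all of the criterion. Nor do the two-monthly examinations in 7.5.2 settle the matter, because that section orders a physical examination and no viral-load test.

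**Conclusion.** The inconsistency is in the text and should be corrected. After week 16 the schedule-based wording gives 12-week testing on drug: 1.5 times the longest recommended interval for HCV (and for HBV on prophylaxis), and 3 times the approximate interval for HBV without prophylaxis. Delayed recognition is supported only for past HCV with undetectable RNA and for HBV-DNA/HBsAg-negative, antibody-positive patients. It arises only at a site that follows the schedule table and not 6.3.3.

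The practical reach is small. Enrollment is complete, and the Amendment 7 rationale reports two patients still on drug at 23 July 2013, with hepatitis status not given. Section 5.1 also excludes liver disease likely to compromise participation. No endpoint, sample size or analysis is affected.

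The conclusion assumes that the visible column headings and footnote 12 describe the follow-up visits correctly, and that the unseen hepatitis rows carry no separate interval. If they do carry one that matches 6.3.3, only the wording of footnote XX and 7.2 remains to be tidied.

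**What to change.** In footnote XX, replace the reference to the visit schedule with:
- HBV-DNA at the intervals in Table 6-4;
- for past HCV with undetectable RNA, HCV-RNA PCR every 4 to 8 weeks;
- for detectable HCV-RNA, ALT every 4 to 8 weeks (6.3.3);
- between visits after week 16 where needed.

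Align the HCV sentence in 7.2 with this. Separating the two HCV groups matters: 6.3.3 asks for monitoring without naming PCR and defines reactivation by ALT alone when RNA is detectable. A blanket PCR rule would add draws that do not detect reactivation as defined for that group.

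The cost is one footnote, one sentence and some blood draws. After week 16, up to week 52:
- Antibody-positive HBV without prophylaxis: 9 − 3 = 6 extra draws.
- Past HCV with undetectable RNA, and HBV on prophylaxis: at least 4 − 3 = 1 extra draw in total, with three draws off-visit (weeks 24, 32, 48). If the visit draws are kept and weeks 22, 34 and 46 added, that is 6 − 3 = 3 extra draws at 6-week spacing.
- Detectable HCV-RNA: ALT tests between visits may be additional. Their number cannot be given, because the laboratory schedule after week 16 is not visible.
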